4.3.2. Replacement of Subjects

During dose escalation in Phase 1, up to 4 subjects per cohort will be enrolled at a time, with the aim of obtaining at least 3 subjects who are evaluable for DLTs (see Section 5.4.2 for definition). If fewer than 3 subjects are evaluable, additional subjects will be enrolled until there are 3 evaluable subjects.

4.4. Duration of Treatment and Subject Participation

After signing the ICF, subject study participation, including screening and post-treatment follow-up is expected to average approximately 12 to 18 months per individual subject. Note that the treatment period will last as long as subjects are deriving benefit, are tolerating the regimen and do not meet withdrawal criteria.

4.5. Overall Study Duration

The study begins when the first subject signs the ICF. The end of the study will occur when all subjects have [REDACTED] been lost to follow-up, or have withdrawn consent for further follow-up. It is anticipated that the study duration will be approximately 3 years.

If there are ≤ 5 subjects on study for more than 6 months, a database lock of the study may occur to allow the analysis of the study data. Any remaining subjects may continue to receive study treatment and be seen by the investigator per the study assessments in Section 6. The remaining subjects are considered to be on study until a discontinuation criterion is met and written notification is provided to the sponsor.

4.6. Study Termination

The investigator retains the right to terminate study participation at any time, according to the terms specified in the study contract. The investigator is to notify the institutional review board (IRB)/independent ethics committee (IEC) in writing of the study's completion or early termination, send a copy of the notification to the sponsor or sponsor's designee, and retain 1 copy for the site study regulatory file.

The sponsor may terminate the study electively or if required by regulatory decision. If the study is terminated prematurely, the sponsor will notify the investigators, the IRBs and IECs, and regulatory bodies of the decision and reason for termination of the study.

4.6.1. Protocol Amendment (Version) 2

As of this Protocol Amendment (Version) 2, enrollment of subjects into any part of Study INCB 01158-202 is halted. This is based on the results from the ECHO-301/KEYNOTE-252 melanoma clinical study (Long et al 2018). In an interim analysis, the study did not meet the prespecified endpoint of improvement in progression-free survival for the combination of pembrolizumab and epacadostat compared with pembrolizumab and placebo. The overall survival endpoint was also not expected to reach statistical significance. There were no safety concerns with the treatment (pembrolizumab + epacadostat) arm compared with the control (pembrolizumab + placebo) arm.

Given the outcome of study ECHO-301/KEYNOTE-252, the changes to the INCB 01158-202 study design are summarized below:

- The ongoing Phase 1 portion (dose escalation and safety evaluation of INCB001158 in combination with epacadostat and pembrolizumab) will stop further enrollment, except for patients who have consented and are in screening as of 08 MAY 2018. These subjects will be permitted to enroll if eligibility is determined as outlined per the Protocol.
- The Phase 1 backfill cohorts and the Phase 2 portion of the study (Part A – tumor expansion of INCB001158 + epacadostat + pembrolizumab and Part B – tumor expansion of INCB001158 + epacadostat) will not be opened.
- Ongoing Phase 1 subjects may continue treatment with INCB001158 + epacadostat + pembrolizumab as long as, per the Protocol, they are deriving clinical benefit, tolerating the treatment, and do not meet any withdrawal criteria.

Sections of the Protocol relating to the parts of the study that will no longer be conducted are now not applicable and should be ignored.

5. TREATMENT

5.1. Treatment Assignment

5.1.1. Subject Numbering and Treatment Assignment

Each subject will be identified in the study by a subject ID number, which is a combination of the site ID and subject number. Site staff should contact the IRT to obtain the subject ID number and confirm a slot is available during prescreening. This subject ID number will be maintained throughout the study and will not be reassigned. The site staff will contact the IRT to enroll the subject and obtain the study drug and treatment group assignment. All subsequent cycles will follow this process. The IRT will also be contacted for ordering study drug supplies and when subjects are discontinued from treatment. Full details will be provided in the IRT manual.

5.1.2. Randomization and Blinding

Not applicable, as this is an open-label study.

5.2. Study Drugs and Other Study Treatments

Study treatment is defined as any investigational treatment(s) or marketed product(s) intended to be administered to a study subject according to the study Protocol. There are 3 investigational study treatments in this study – INCB001158, epacadostat, and pembrolizumab (Table 7).

INCB001158 is also referred to as the study drug in this Protocol. Although pembrolizumab is approved and marketed in various indications (see Section 1.1.3.1), it is investigational in this study in combination with INCB001158 and epacadostat.

Table 7: Study Drug and Other Study Treatments

Drug	Dose	Dose Frequency	Route of Administration	Regimen/Treatment Period
INCB001158	25-150 mg ^a	BID	Oral	Phase 1 and Phase 2 Part A : Daily until meets discontinuation criteria or for 35 cycles ^b , whichever is sooner Phase 2 Part B : Daily until meets discontinuation criteria
Epacadostat	50-100 mg ^a	BID	Oral	Phase 1 and Phase 2 Part A : Daily until meets discontinuation criteria or for 35 cycles ^b , whichever is sooner Phase 2 Part B : Daily until meets discontinuation criteria
Pembrolizumab	200 mg	Every 3 weeks	IV infusion	Phase 1 and Phase 2 Part A : Day 1 of each cycle until meets discontinuation criteria or for up to 35 cycles ^b , whichever is sooner

^a See Section 4.1.1 for details of dose levels of INCB001158 and epacadostat during the Phase 1 dose escalation.

^b A cycle length of 21 days.

5.2.1. INCB001158

5.2.1.1. Description and Administration

INCB001158 will be administered orally using a capsule (25 mg or 100 mg per capsule) formulation. INCB001158 will be administered only to subjects who have signed and dated an ICF. INCB001158 will be administered on Days 1 through 21 of each 21-day cycle and should be taken orally using the number of capsules directed in the Pharmacy Manual. The starting dose will depend on which phase of the study the subject is in. In Phase 1, the starting dose will be based on which dose level cohort the subject is in; in Phase 2, the starting dose will be the RP2D identified in Phase 1. INCB001158 dosing will not be adjusted for body weight or surface area.

In Phase 1 and Phase 2 Part A, INCB001158 and epacadostat will be given daily in combination with pembrolizumab for up to 35 cycles, as long as disease progression has not occurred and criteria for treatment discontinuation have not been met.

In Phase 2 Part B, INCB001158 and epacadostat will be given daily for as long as disease progression has not occurred and criteria for treatment discontinuation have not been met.

5.2.1.2. Supply, Packaging, and Labeling

INCB001158 will be provided to sites by Incyte. The contents of the label will be in accordance with all applicable regulatory requirements.

INCB001158 will be supplied as 25 mg or 100 mg capsules packaged in blister cards. No preparation is required. All capsule excipients comply with the requirements of the applicable compendial monographs (Ph Eur, USP/NF; refer to [iIB](#)).

All Incyte investigational product labels will be in the local language and will comply with the legal requirements of each country.

5.2.1.3. Storage

Blister cards of INCB001158 capsules should be stored at room temperature, 15°C to 30°C (59°F to 86°F).

5.2.1.4. Instruction to Subjects for Handling Study Drug (INCB001158)

The subject must be instructed in the handling of study drug as follows:

- To store the study drug at room temperature.
- To only remove from the study drug blister card the number of capsules needed at the time of administration.
- Not to remove doses in advance of the next scheduled administration.
- To make every effort to take doses on schedule.
- To report any missed doses.

- To take study drug at approximately the same times each day without respect to food (except on Protocol-defined clinic days, when the subject should fast for at least 8 hours before taking study drug; see Section 7.6.5.2) and with a full glass of water. The second dose on any given day should be taken approximately 12 hours after the first dose.
- Subjects who vomit their INCB001158 dose should be instructed NOT to make up that dose and to report the frequency of vomiting occurrences associated with study drug administration to the site. Subjects who report ≥ 3 incidences of vomiting associated with study drug administration will have a blood sample drawn for an unscheduled PK analysis.
- To keep study drug in a safe place and out of reach of children.
- To bring all used and unused study drug blister cards to the site at each visit.
- Missed doses of INCB001158 should be skipped. If a subject forgets to take a dose of study drug and he/she is outside of the allotted window period (± 6 h), then he/she should be instructed to skip that dose and NOT to take extra study drug at their next administration.
- On Protocol-defined clinic days (see Table 14) subjects should be instructed NOT to take their morning dose of INCB001158 at home. The morning dose must be administered at the clinical site after all predose procedures have been performed. The time of dose administration will be recorded in the clinic. The evening doses will be self-administered by the subject after all postdose activities have been completed.

5.2.2. Epacadostat

Epacadostat 25 mg or 100 mg tablets will be self-administered orally BID. All BID doses will be taken morning and evening, approximately 12 hours apart without respect to food. If a dose is missed by more than 4 hours, that dose should be skipped and should be resumed at the scheduled time. Dose reductions or interruptions may be required for safety, see Section 5.4.

5.2.2.1. Description and Administration

Epacadostat 25 mg or 100 mg tablets will be self-administered orally BID. All BID doses will be taken morning and evening, at the same time as the INCB001158 dose, approximately 12 hours apart, without respect to food. If a dose is missed by more than 4 hours, that dose should be skipped and should be resumed at the next scheduled time. Dose reductions or interruptions may be required for safety; see Section 5.4. Subjects will hold the morning dose of epacadostat for each clinic visit; study medication will be administered in the clinic.

In Phase 1 and Phase 2 Part A, epacadostat may be taken in combination with INCB001158 and pembrolizumab for up to 35 cycles as long as disease progression has not occurred and criteria for treatment discontinuation have not been met.

In Phase 2 Part B, epacadostat and INCB001158 will be given daily for as long as disease progression has not occurred and criteria for treatment discontinuation have not been met.

5.2.2.2. Supply, Packaging, and Labeling

Epacadostat will be provided to sites by Incyte. The contents of the label will be in accordance with all applicable regulatory requirements.

Epacadostat will be supplied as 25 mg and 100 mg tablets packaged in high-density polyethylene bottles. All tablet excipients comply with the requirements of the applicable compendial monographs (Ph Eur, USP/NF; refer to [eIB](#)).

5.2.2.3. Storage

Bottles of tablets should be stored at room temperature, 15°C to 30°C (59°F to 86°F).

5.2.2.4. Instruction to Subjects for Handling Epacadostat

The subject must be instructed in the handling of epacadostat study treatment as follows:

- To store the study treatment at room temperature.
- To only remove from the study treatment bottle/kit the number of tablets needed at the time of administration.
- To make every effort to take doses on schedule.
- To report any missed doses.
- Subjects who vomit their epacadostat dose should be instructed NOT to make up that dose and to report the frequency of vomiting occurrences associated with study drug administration to the site. Subjects who report ≥ 3 incidences of vomiting associated with epacadostat administration will have a blood sample drawn for an unscheduled PK analysis.
- To keep study treatment in a safe place and out of reach of children.
- To bring all used and unused study treatment kits to the site at each visit.
- If a dose is missed by more than 4 hours, that dose should be skipped, and the next scheduled dose should be administered at the usual time.

5.2.3. Pembrolizumab

5.2.3.1. Description and Administration

Study treatment with pembrolizumab (Phase 1 and Phase 2 Part A only) should be administered on Day 1 of each cycle after all procedures/assessments have been completed. All study treatments will be administered on an outpatient basis.

Study treatment of pembrolizumab may be administered up to 3 days before or after the scheduled Day 1 of each cycle due to administrative reasons except for Cycle 1 Day 1, where there is no window.

Pembrolizumab will be administered as a dose of 200 mg using a 30-minute IV infusion, to start directly after the AM doses of INCB001158 and epacadostat. Sites should make every effort to target infusion timing to be as close to 30 minutes as possible. However, given the variability of

infusion pumps from site to site, a window of -5 minutes and +10 minutes is permitted (ie, infusion time is 30 minutes -5 min/+10 min).

Pembrolizumab in combination with INCB001158 and epacadostat may be taken for up to 35 cycles as long as disease progression has not occurred.

5.2.3.2. Supply, Packaging, and Labeling

Pembrolizumab is supplied either as 50 mg lyophilized powder for reconstitution in single-use vials or as 25 mg/mL sterile solution for infusion in 4 mL vials. The Pharmacy Manual contains specific instructions for pembrolizumab, for reconstitution of the lyophilized powder, preparation of the infusion fluid, and administration.

5.2.3.3. Storage

Vials of pembrolizumab must be stored under refrigeration at 2°C to 8°C (36°F to 46°F) in the original carton to protect them from light. Do not freeze. Do not shake.

5.3. Treatment Compliance

Compliance with all study-related treatments should be emphasized to the subject by the site personnel, and appropriate steps should be taken to optimize compliance during the study. Compliance with INCB001158 and epacadostat will be calculated by the sponsor based on the drug accountability documented in the patient diaries and by the site staff and will be monitored by the sponsor/designee (capsule/tablet counts). Subjects will be instructed to bring all study treatments with them to the study visits from Cycle 2 Day 1 onwards, in order for site personnel to conduct capsule/tablet counts to assess study treatment accountability. The drug accountability documentation will be used by the sponsor to calculate treatment compliance.

Pembrolizumab is administered as an IV infusion by site personnel. Receipt of infusions will be documented by the site staff and monitored by the sponsor/designee.

5.4. Treatment Interruptions and Adjustments

5.4.1. Dose Modifications

Selections and modifications to the study treatment regimen are planned for dose-escalation cohorts in Phase 1. Dose interruptions and modifications also may occur for individual study subjects. The identification of DLTs will define the doses used in planned cohorts (see Section 4.1.1). Further, the occurrence of DLTs and other toxicities (related or unrelated to study treatment) will guide decisions for treatment interruptions and discontinuation for individual subjects. Dose modifications should not be made during the DLT observation period without discussion with the medical monitor. Intrasubject dose escalation will not be permitted.

5.4.1.1. INCB001158

For subjects in Phase 1, dose reductions of INCB001158 will be permitted during the first 2 cycles (first 42 days) only if a subject experiences a DLT or a toxicity that may herald a DLT. If a subject experiences a DLT, treatment continuation at a lower dose of INCB001158 will be permitted as long as the toxicity has returned to ≤ Grade 1 or baseline within 28 days. When

INCB001158 is held or discontinued, epacadostat and pembrolizumab therapy may be continued, at the investigator's discretion. Upon recovery, subjects may restart at 1 INCB001158 dose level lower. Subjects who do not recover within 28 days will not be eligible for resumption of study treatment without approval from the medical monitor. After Cycle 2, dose reductions or interruptions for AEs may take place at any time at the discretion of the investigator in consultation with the medical monitor. See also [Table 9](#).

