5.4.1.3. Pembrolizumab

In Phase 1 and Phase 2 Part A, pembrolizumab may be interrupted, but no dose modifications are permitted. In all cases where pembrolizumab dosing is held, dosing for INCB001158 and epacadostat must also be held. However, if either or both of INCB001158 and epacadostat is/are discontinued due to drug-related AEs, subjects are allowed to continue to receive the other study treatments. See also [Table 9](#).

5.4.2. Dose-Limiting Toxicity and Determination of Maximum Tolerated Dose in Phase 1

Dose-limiting toxicity will be defined as the occurrence of any of the toxicities in [Table 8](#) occurring up to and including Day 42, except those with a clear alternative explanation (eg, disease progression) or transient (≤ 72 hours) abnormal laboratory values without associated clinically significant signs or symptoms based on investigator determination. All DLTs will be assessed by the investigator using CTCAE v4.03 criteria. Subjects who receive at least 63 of 84 doses ($\geq 75\%$) for each of INCB001158 and epacadostat at the level assigned plus at least 2 doses of pembrolizumab or who have a DLT, will be considered evaluable for determining tolerability of the dose. Subjects who do not meet these criteria may be replaced to obtain sufficient evaluable subjects to be able to assess that dose level using the BOIN design, as outlined in [Table 2](#).

Clear evidence of urea cycle inhibition (eg, an increase in fasting urinary orotic acid to $> 10 \times \text{ULN}$, any orotic acid value of $> 40 \times \text{ULN}$, or symptomatic hyperammonemia) would also be considered a dose-limiting event and will be treated the same as a DLT with regard to the dose escalation rules and definition of the MTD described in Section 4.1.1. Refer to the INCB001158 IB ([iIB](#)) for an explanation of these orotic acid thresholds.

Individual subject dose reductions for INCB001158 and epacadostat may be made based on events observed at any time during treatment; however, for the purposes of dose cohort escalation/de-escalation, expanding a dose cohort, and determining the MTD of INCB001158, decisions will be made based on events that are observed from the first day of study treatment administration through and including the final day of Cycle 2 (Day 42). A lower MTD may subsequently be determined based on relevant toxicities that become evident after Day 42.

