If a subject experiences a DLT that is considered life-threatening, permanently discontinue all 3 study treatments. If a subject experiences a DLT that is not considered life-threatening, interrupt all 3 study treatments, and follow the management guidelines in [Table 9](#).

Table 8: Definition of Dose-Limiting Toxicity

Toxicity
Nonhematologic

 • Any \geq Grade 3 nonhematologic toxicity EXCEPT: 
 – Transient (\leq 72 hours) abnormal laboratory values without associated clinically significant signs or symptoms. – Nausea, vomiting, and diarrhea adequately controlled with medical therapy within 48 hours. – An event clearly associated with the underlying disease, disease progression, a concomitant medication, or comorbidity. – Asymptomatic changes in amylase, lipase, or lipid profiles. – Singular or nonfasting elevations in blood glucose (ie, blood glucose excursions will be considered toxicities if fasting blood glucose is elevated on 2 separate occasions).
Hematologic

 • Grade 3 thrombocytopenia with bleeding. • Grade 4 thrombocytopenia. • Febrile neutropenia (ANC $<$ $1.0 \times 10^9/L$ and fever $>$ $101^\circ F/38.5^\circ C$). • Grade 4 neutropenia that does not recover to \leq Grade 2 in \leq 7 days after interrupting study treatment. • Grade 4 anemia.
Immune-related toxicity

 • \geq Grade 2 ocular irAEs will be considered a DLT. • Grade 3 irAEs that do not improve to baseline or at least Grade 1 in $<$ 5 days with appropriate care or with corticosteroid therapy will be considered a DLT. Exception: Grade 3 rash in the absence of desquamation, no mucosal involvement, does not require systemic steroids, and resolves to Grade 1 by the next scheduled dose of pembrolizumab or 14 days, whichever is longer. • Grade 4 irAEs will be considered a DLT regardless of duration. • \geq Grade 2 pneumonitis.
General

 • The inability to receive \geq 75% of INCB001158 and/or epacadostat doses and/or 2 doses of pembrolizumab during the DLT-evaluation period (42 days) due to a drug-related AE will be considered a DLT. • Any other AE that is felt to be treatment-limiting in the medical opinions of the principal investigator and the medical monitor may be considered a DLT.

ANC = absolute neutrophil count.

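### Section 5.4.1.1 permits INCB001158 again after any Phase 1 DLT, including a life-threatening one, although Section 5.4.2 then stops all three drugs; two partner-drug permissions conflict with 5.4.2 more narrowly

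*Combined protocol and SAP*

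**What the plan says.** Three places in the protocol tell the site what to do with study treatment after a DLT.

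- **Section 5.4.1.1 (INCB001158).** "If a subject experiences a DLT, treatment continuation at a lower dose of INCB001158 will be permitted as long as the toxicity has returned" to Grade 1 or less, or baseline, within 28 days; the restart is one INCB001158 dose level lower. For a subject without recovery: "Subjects who do not recover within 28 days will not be eligible for resumption of study treatment without approval from the medical monitor". On the partner drugs, when "INCB001158 is held or discontinued, epacadostat and pembrolizumab therapy may be continued", this is at the investigator's discretion.
- **Section 5.4.1.3 (pembrolizumab).** If "either or both of INCB001158 and epacadostat is/are discontinued due to drug-related AEs, subjects are allowed to continue to receive the other study treatments".
- **Section 5.4.2 (DLT definition and MTD).** "If a subject experiences a DLT that is considered life-threatening, permanently discontinue all 3 study treatments". For the rest: "If a subject experiences a DLT that is not considered life-threatening, interrupt all 3 study treatments, and follow the management guidelines in" Table 9.

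Sections 5.4.1.1 and 5.4.1.3 cross-refer to Table 9, not to Section 5.4.2.

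**The concern.** Section 5.4.1.1 speaks of a DLT without regard to severity, and its only condition for the lower-dose restart is recovery: "as long as the toxicity has returned to ≤ Grade 1 or baseline within 28 days". A life-threatening event can meet that condition. An investigator who reads 5.4.1.1 and follows its pointer to Table 9 has no signal that a stricter rule sits in 5.4.2. The subject could be given INCB001158 again, or kept on the partner drugs, when 5.4.2 requires all three to stop.

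The 5.4.2 rule is deliberate. Appendix D (Amendment 1, item 4) records it as an FDA request, and the current 5.4.2 text matches that entry. The log is cited here only for intent.

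**Working it through.** The main question is one of rules, not arithmetic. For each kind of event through Day 42, compare what 5.4.1.1 or 5.4.1.3 permits with what 5.4.2 requires.

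| Event and drug | Permission | Section 5.4.2 | Result |
|---|---|---|---|
| Life-threatening DLT, recovered within 28 days; INCB001158 | 5.4.1.1: restart one level lower | Stop all three for good | Conflict |
| Life-threatening DLT, not recovered; INCB001158 | 5.4.1.1: resume if the medical monitor approves (implied) | Stop all three for good | Conflict |
| Life-threatening DLT; remaining drugs | 5.4.1.1 and 5.4.1.3: may continue | Stop all three for good | Conflict |
| Other DLT; INCB001158 | 5.4.1.1: restart one level lower on recovery | Interrupt all three, then Table 9 | Compatible |
| Other DLT; partners under 5.4.1.1 | May continue while INCB001158 is held or discontinued | Interrupt all three first | Conflict during the interruption |
| Other DLT; remaining drugs under 5.4.1.3 | May continue once INCB001158 and/or epacadostat is discontinued | Interrupt all three, then Table 9 | Conflict only if they are not interrupted first |
| Event that is not a DLT | Remaining drugs may continue | Does not apply | Compatible |

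**Does other text settle the order?** Section 5.5.1 makes withdrawal mandatory for unacceptable toxicity, but cites 5.4.6, 5.4.9 and 5.4.10, not 5.4.2. Section 5.4.10 rests on judgment, on more than two dose reductions, or on length of delay. None of these necessarily catches a life-threatening DLT that resolves quickly. Section 5.4.2 sends only the DLTs that are not life-threatening to Table 9, so it does set the order between itself and Table 9. It does not do so for 5.4.1.1.

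**Effect on the design.** Under 5.4.2 a subject with a DLT is evaluable and is counted. Later treatment does not alter that count, so the BOIN decisions are the same under either section.

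**Reach.** Section 4.3.1 allows up to 5 Phase 1 subjects. Section 4.6.1 lets subjects in screening on 08 MAY 2018 enroll, and Section 6.2 puts Cycle 1 Day 1 no more than 21 days after consent. Assume the last consent was on 08 MAY and that there was no repeat screening:

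- Latest Cycle 1 Day 1: 08 MAY + 21 days = 29 MAY 2018.
- Day 42: 29 MAY + 41 days = 09 JUL 2018, which is 38 days after Amendment 2 (01 JUN 2018).

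Earlier consent shortens this. It bounds when a DLT can occur, not when a restart can be decided.

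**How wide can a Table 9 footnote be?** A note that interrupts all three drugs for every Table 8 DLT, whatever the row says, would reach into the urea-cycle row, which withholds INCB001158 and continues both partners. Table 8 counts as a DLT the inability to take at least 75% of INCB001158 doses because of a drug-related AE. Section 5.4.2 sets this at 63 of 84 doses over 42 days, two per day, so up to 84 − 63 = 21 doses can be missed.

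- An 11-day hold misses 22 doses: 62/84 = 73.8%, below 75%.
- A 14-day hold misses 28 doses: 56/84 = 66.7%.

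A drug-related urea-cycle hold of about 11 days can therefore become a Table 8 DLT, and the broad note would then override the row. Section 5.4.2 says that urea-cycle dose-limiting events "will be treated the same as a DLT with regard to the dose escalation rules and definition of the MTD". It does not say there that the partner drugs must stop.

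**The case against.** The strongest reply is that this is a missing cross-reference rather than a contradiction. Section 5.4.1.1 only permits; 5.4.2 commands, and is the more specific rule for life-threatening events. A site that obeys 5.4.2 breaches nothing in 5.4.1.1. That is the sensible reading and the result wanted here. But no sentence states it, and 5.4.1.1 is itself written about DLTs, so its reader has no reason to think it incomplete.

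The second reply is that safeguards already exist, and they do:

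- Dose modifications in the DLT period need discussion with the medical monitor (5.4.1).
- The sponsor and investigators jointly adjudicate high-grade AEs as dose-limiting (5.4.5).
- Sections 5.4.10 and 5.5.1 stop treatment that is judged not to be in the subject's interest or injurious.
- Table 9 permanently stops epacadostat and pembrolizumab for Grade 4 pneumonitis, colitis, hepatic and renal events, rash, and the residual irAE category.

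These lower the risk considerably, most of all for the partner drugs. None of them says which section governs.

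The reply also succeeds on scope. A reader might infer that the partner-drug permissions clash with 5.4.2 for every DLT. The documents do not support that: after a DLT that is not life-threatening, all three drugs can be interrupted and the remaining ones resumed under Table 9, which satisfies both 5.4.2 and 5.4.1.3.

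**Conclusion.** The conflict is real and should be corrected. For a life-threatening DLT, 5.4.1.1 permits INCB001158 to be given again, and 5.4.1.1 and 5.4.1.3 permit the remaining drugs to continue, where 5.4.2 stops all three. For other DLTs, the partner-drug sentence in 5.4.1.1 conflicts during the required interruption, and 5.4.1.3 conflicts only if that interruption is skipped. Restarting INCB001158 lower after a DLT that is not life-threatening is consistent with 5.4.2.

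The reach is up to 5 subjects and DLTs through Day 42. The 09 JUL 2018 date rests on the consent and screening assumptions stated in the check.

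Two stronger inferences are not supported. A reader might add the 28-day window to Day 42 and take Day 70 as the last possible restart decision. Section 5.4.1.1 leaves room for resumption without recovery, and does not say when the 28 days begin, so no outer limit follows. A reader might also suspect damage to the dose-escalation design; the DLT count is unaffected. This is a subject-safety and consistency matter, not a statistical error.

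**What to change.** - **Section 5.4.1.1:** limit both the lower-dose continuation and the resumption with medical monitor approval to DLTs not considered life-threatening. Make the partner-drug sentence subject to Section 5.4.2.
- **Section 5.4.1.3:** make the permission to continue the remaining treatments subject to Section 5.4.2.
- **Table 9 (optional):** add a footnote that says only that, after a life-threatening DLT, Section 5.4.2 applies and no study treatment is restarted or re-challenged. It should not override Continue entries for other DLTs, for the reason shown with the urea-cycle row.

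Under Section 10.1 a change to Protocol procedures needs sponsor and then IRB/IEC approval, after which the 4 planned Phase 1 sites must be told. The change needs no new decision on restart dose and leaves the design, sample size and analysis as they are.
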